7.11.1 Primary Endpoint

The primary endpoint of the study is the change in *S. aureus* log₁₀ CFU/mL from baseline to immediately prior to surgery.

The baseline value is defined as the swab collected prior to the first dose of study drug at approximately 24 hours prior to surgery. The immediately prior to surgery value is defined as the pre-surgery swab collected up to 1 hour prior to surgery which is obtained following three doses of study drug and prior to the fourth dose of study drug.

Primary Analysis

The change in *S. aureus* log₁₀ CFU/mL from baseline to immediately prior to surgery will be analyzed using an analysis of covariance (ANCOVA). The model will be fitted with the change in *S. aureus* log₁₀ CFU/mL from baseline to immediately prior to surgery as the dependent variable and treatment group and country as fixed effects. The baseline *S. aureus* log₁₀ CFU/mL value will be included as a covariate.

Adjusted Least square means (LS Means) for the placebo and 0.2% w/w XF-73 treatment groups estimated by the model will be presented, together with the associated standard errors (SE). The adjusted LS Mean, SE and 95% CI and two-sided p-value of the treatment difference will also be presented. All estimates provided by the ANCOVA model will be presented on the log₁₀ scale.

The assumption is that the log10 CFU data are normally distributed. This assumption will be assessed using a Shapiro-Wilks' test alongside a visual inspection of the residual plots. If this assessment indicates a departure from log-normality, additional data transformations or a non-parametric analysis will be considered for further analysis post-hoc, as appropriate.

Sensitivity Analysis

In addition to the planned analysis in the PPS which requires patients to receive at least 4 doses of pre-surgery treatment, a sensitivity analysis will be performed which

will include all patients who receive at least 3 doses of pre-surgery treatment to confirm the main analysis conclusions.

A Mixed Model for Repeated Measures (MMRM) using all available data will be fitted in order to estimate the change from baseline to immediately prior to surgery. Further details on the model fitted can be found in Section 6.11.2.3 of this SAP.

Where conclusions resulting from these analyses provide substantive differences in the conclusions drawn, imputation methods may be used and additional analyses may also be considered for key secondary endpoints.

Summaries

Descriptive statistics including the geometric mean and geometric co-efficient of variation will be presented for all observed *S. aureus* CFU/mL values for each pre-surgery and post-surgery swab collected (baseline, prior to the third dose of study drug, immediately prior to surgery, within 1 hour of incision closure, 48 hours after surgery and 6 days after surgery). The change from baseline values will also be presented and summarized by CFU category. For both the observed and the change from baseline, descriptive statistics for the log-transformed values will also be presented (geometric mean and co-efficient of variation will not be presented as these are not relevant for log transformed data).

Box and whisker plots will be presented for each treatment group for the change from baseline in *S. aureus* log₁₀ CFU/mL over time. The change in S. *aureus* log CFU/mL from baseline versus observed baseline S. *aureus* log CFU/mL will also be presented in a scatterplot.

The observed *S. aureus* CFU/mL and log₁₀ CFU/mL values will be listed.

7.11.2 Secondary Endpoints

7.11.2.1 AUC of *S. aureus* from baseline to pre-surgery

An AUC of *S. aureus* CFU/mL will be calculated using the values collected at baseline, prior to the third dose of study drug and immediately prior to surgery. Data on the original scale will be used to determine the AUC. The AUC will be calculated using the trapezoidal method and will be log₁₀-transformed for analysis.

The formula for the trapezoidal method is below:

	Baseline	Prior to the third dose	Immediately prior to surgery
Time	t ₁	t_2	t ₃
Response	а	b	С

AUC =
$$(t_2-t_1)(a+b) + (t_3-t_2)(b+c)$$

2

AUC will only be calculated where a patient has non-missing results at both the baseline and immediately prior to surgery time points. An ANCOVA model will be fitted and presented as described in Section 6.11.1 where the baseline *S. aureus* log₁₀ CFU/mL value will be included as the covariate and treatment group and site as fixed effects. If there is evidence that there is a departure from the assumptions of normality alternative transformations such as AUC of log₁₀ S. *aureus* CFU/mL will be considered.

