2.2 Study Endpoints

The primary endpoint of the study is the change in *S. aureus* log CFU/mL from baseline to pre-surgery.

The secondary endpoints are:

- Difference in AUC of S. aureus log CFU/mL from baseline to pre-surgery.
- Difference in AUC of S. aureus log CFU/mL from baseline to immediately post-surgery.
- Change in S. aureus log CFU/mL from baseline to immediately after surgery.
- Change in S. aureus log CFU/mL from baseline to 48 hours after surgery.
- Change in S. aureus log CFU/mL from baseline to 7 days after surgery.
- Percentage of patients reaching a specific reduction in S. aureus carriage prior to surgery, immediately post-surgery and on Day 6 ± 24hrs.
- Difference in the incidence of *S. aureus* post-operative infections during the 30-day period after surgery (90 days in the case of foreign implant).
- Incidence of Treatment Emergent Adverse Events (TEAEs) from the first dose of study medication to 7 days post last application of study medication.
- Changes in vital signs, safety clinical laboratory assessments, nasal examination and smell identification test.

The exploratory endpoint is the reason for post-operative prescribed anti-staphylococcal antibiotic use during the 30-day post-operative period (90 days in the case of an object implant).

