7.10 Administration of Study Drug and Exposure

Treatment exposure will be summarized by treatment group and will include the total number of patients and percentage of patients with each number of doses applied. Compliance will also be included in the summary table where a compliant subject is defined as having received all 5 doses of study drug all within the acceptable dosing windows.

Acceptable dosing windows for each dose are as follows:

- First dose: 22 hours ±2 hours before estimated incision time.
- Second dose: 14 hours ±2 hours before estimated incision time.
- Third dose: 6 hours ±2 hours before estimated incision time.
- Fourth dose: Within 1 hour before incision time.
- Fifth dose: Within 1 hour of incision closure time.

Details of the doses applied including the total number of doses applied will be listed.

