7.11.2.2 AUC of S. aureus from baseline to post-surgery

An AUC of *S. aureus* CFU/mL including values at all timepoints from baseline to within 1 hour of incision closure will be calculated. This AUC will include the following time points: at baseline, prior to the third dose, immediately prior to surgery and within 1 hour of incision closure. The AUC will be calculated as described in section 6.11.2.1 using the trapezoidal method where the equation will be expanded to include the appropriate post-surgery time point as:

AUC =
$$(t_2-t_1)(a+b) + (t_3-t_2)(b+c) + ... + (t_n-t_{n-1})(r_{n-1}+r_n)$$

where t_n and r_n are the time and the response at the post-surgery timepoint respectively. The AUC will be log_{10} -transformed for analysis. AUC will only be calculated where a patient has non-missing results at all of the following time points: baseline, immediately prior to surgery and within 1 hour of incision closure.

An ANCOVA model will be fitted and presented as described in Section 6.11.1 where the baseline *S. aureus* log₁₀ CFU/mL value will be included as the covariate and treatment group and site as fixed effects.

Summaries

Descriptive statistics will be presented for the pre-surgery AUC and the post-surgery AUC.

Box and whisker plots will be presented for each treatment group for the AUC of *S. aureus* log₁₀ CFU/mL over time.

The calculated AUC values will be listed on both the observed and log₁₀ scale.

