7.14 Changes from the Protocol Planned Analysis

For the analysis of the change in log10 CFU from baseline to post-surgery an MMRM model has been chosen in favor of the ANCOVA specified in protocol section 11.7.

The AUC of S. aureus from baseline to pre-surgery will be calculated using values on the original scale and will then be log₁₀-transformed, as opposed to calculating the AUC on the log₁₀-transformed values as described in protocol section 11.7.

The proportional odds model described in protocol section 11.7 for the nasal carriage according to SQS has been removed. Summary statistics are deemed to be sufficient.

Any reference to the modified Intent-to-Treat (mITT) set has been removed from the SAP as analysis will no longer be performed in this population.

The major protocol deviations leading to exclusion from the PPS has been clarified in Section 7.4. Major protocol deviations are defined more broadly in the protocol, so include deviations which are important to report, but would not impact the evaluation of efficacy. Therefore, the SAP has made clear that only those major protocol deviations considered to impact the evaluation of efficacy (i.e. deemed important) will be excluded from the PPS.

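### Both secondary AUC endpoints are defined on log CFU/mL but calculated on raw CFU/mL and logged afterwards, a different quantity that compresses large reductions in carriage

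*SAP*

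**What the plan says.** SAP 2.2 lists the endpoint as "Difference in AUC of S. aureus log CFU/mL from baseline to pre-surgery", with a matching endpoint running to immediately after surgery. The protocol synopsis and protocol 5.2 name the same two endpoints on the log scale.

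The calculation is specified differently:

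- **SAP 7.11.2.1 (pre-surgery AUC):** "Data on the original scale will be used to determine the AUC". It continues: "The AUC will be calculated using the trapezoidal method and will be log", so log10 is applied to the finished area.
- **SAP 7.11.2.2 (post-surgery AUC):** "The AUC will be calculated as described in section 6.11.2.1 using the trapezoidal method". That number is the old label of 7.11.2.1, left from before the sections were renumbered. This area is also log10-transformed afterwards.
- **Model for both:** ANCOVA with baseline log10 CFU/mL as covariate.
- **Fallback:** 7.11.2.1 says an AUC of log10 values will be considered if normality looks doubtful. 7.11.2.2 does not repeat this.
- **Plots:** the summaries in 7.11.2.2 plan box plots of the AUC of log10 CFU/mL, which on its wording is not the quantity tested.
- **Declared change:** SAP 7.14 states "The AUC of S. aureus from baseline to pre-surgery will be calculated using values on the original scale" and then log10-transformed. It contrasts this with protocol 11.7, gives no reason, and does not mention the post-surgery AUC.

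**The concern.** The log of an area under raw counts is not the area under log counts. On the raw scale a tenfold fall removes 90% of a swab's contribution and a hundredfold fall removes 99%, so deeper kills add almost nothing. What is left in a well-treated patient is mainly the pre-dose baseline term, and baseline is also the model covariate.

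Two things are at stake. The reported result would not estimate the endpoint that the protocol and SAP 2.2 name. Its size would also understate the difference between a moderate reduction and near-eradication. Because these endpoints are descriptive, the size of the estimate is what a reader will use.

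**Working it through.** **Inputs from the documents.**

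- Baseline swab, before dose 1: "First dose: 22 hours ±2 hours before estimated incision time" (SAP 7.10), so about -22 h.
- Second swab, before dose 3: "Third dose: 6 hours ±2 hours before estimated incision time" (SAP 7.10), so about -6 h.
- Third swab: "pre-surgery swab collected up to 1 hour prior to surgery" (SAP 7.11.1), taken here as -1 h.
- Zero counts are set to 1 CFU/mL (SAP 7.11).
- Planning values: 40 per arm, SD 2 log10, differences of 1.5 and 2 log10, two-sided 0.05 (protocol 11.10, SAP 3).

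**The plan's own figure.** No power is stated for the AUCs. For the primary endpoint, SE = 2 × √(2/40) = 0.447 and 1.5/0.447 = 3.35. Power is about Φ(3.35 − 1.96) = 0.92 (0.91 with the noncentral t), which agrees with the stated 90%.

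**Trapezoid weights.** With counts a, b, c at the three swabs:

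AUC = 16(a + b)/2 + 5(b + c)/2 = 8a + 10.5b + 2.5c.

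Unchanged carriage gives 21a. A kill of D log10 at both later swabs gives a × (8 + 13 × 10^−D).

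**Effect against unchanged carriage, no within-patient noise.** The raw-scale effect is log10[21/(8 + 13 × 10^−D)]. The time-averaged log-scale effect is D × 13/21, before the 1 CFU/mL floor.

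| Kill D (log10) | log10 of raw AUC | Share of cap | AUC of log10 values | Baseline share of treated raw AUC |
|---|---|---|---|---|
| 1 | 0.354 | 84% | 0.62 | 86% |
| 1.5 | 0.397 | 95% | 0.93 | 95% |
| 2 | 0.412 | 98% | 1.24 | 98% |
| 4 | 0.419 | 100% | 2.48 | 100% |

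The cap is log10(21/8) = 0.419. With the third swab at 0 h, the weights are 8, 11 and 3 and the cap is log10(22/8) = 0.44. Across the timing windows tried it runs from 0.38 to 0.52. For the post-surgery AUC it is 0.48, 0.51 or 0.54 if the closure swab is assumed to fall 2, 4 or 6 h after incision.

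**Effect with within-patient noise.** The documents do not give the quantities needed, so these are assumptions: baseline mean 3.5 and SD 2 log10, truncated at 0; each later swab equal to baseline minus the kill plus residual noise; correlation 0.8 between the two later residuals; floor at 1 CFU/mL; 40 per arm; baseline-adjusted ANCOVA without a site term.

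| Residual SD | Raw AUC then log10: 1.5 → 4 log kill | AUC of log10 values: 1.5 → 4 log kill |
|---|---|---|
| 0.5 | 0.44 → 0.47 | 0.88 → 1.90 |
| 1 | 0.53 → 0.63 | 0.86 → 1.86 |
| 2 | 0.67 → 1.04 | 0.80 → 1.77 |

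The extra 2.5 log10 of kill adds 0.10 on the raw scale against 1.00 on the log scale at SD 1 (0.63 − 0.53; 1.86 − 0.86). At SD 2 it adds 0.37 against 0.97 (1.04 − 0.67; 1.77 − 0.80).

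**The case against.** The strongest reply has five parts.

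1. **The hard cap needs noise-free swabs.** This stands. A reader might infer that the AUC result barely responds to kill at all. At the planning SD of 2 it does respond: the raw-scale effect goes from 0.48 to 1.04 between a 1 and a 4 log kill. It also responds below about 1 log in every setting. The supportable statement is compression, not insensitivity.

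2. **The log scale is not always more powerful.** This stands. Under the assumptions above, at 1.5 log10 and SD 2, power is about 82% for the raw AUC and 91% for the log AUC. If 20% of post-baseline swabs in both arms are assumed to be sporadic zeros, each set to 1 CFU/mL, the order reverses: about 75% to 79% for raw against 65% to 70% for log, depending on the baseline SD assumed. At 10% zeros the two are about equal. The documents do not give the zero rate, so no general power gain can be claimed.

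3. **The pre-surgery swab's small weight is not caused by the scale.** This stands. Clearance at that swab alone moves the raw result by log10(21/18.5) = 0.055, or 13% of the cap. Its weight in the log AUC is 2.5/21 = 12%. Swab spacing is the cause, and the fix leaves it unchanged.

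4. **The departure is declared and pre-specified, and protocol 11.7 is ambiguous.** This stands in part. The wording of 11.7 alone could mean the log of a raw area, but SAP 7.14 itself reads it as an area of log values, and protocol 5.2 and SAP 2.2 are explicit. The declaration covers one of the two AUCs, and the endpoint definition was left unchanged.

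5. **Depth of kill is shown elsewhere.** True: the primary ANCOVA, the repeated-measures model, the reduction curves and the 2-log-drop summary all report it. This limits the harm, but does not make the AUC analysis match its endpoint.

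Baseline domination also applies only to patients with a substantial kill. In an unchanged carrier the baseline share is 8/21 = 38%.

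**Conclusion.** The concern holds as a mismatch between endpoint and calculation, with compression of large effects as its consequence. The mismatch rests on the text alone. The noise-free cap of 0.42 rests on the nominal swab times (0.38 to 0.52 across the windows tried). The noisy figures rest on the assumed baseline distribution, residual SD and correlation. In all three noise settings the raw-scale effect grows much less with kill than the log-scale effect.

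The normality-triggered fallback is not a remedy. Compression is not a failure of normality, the switch would let the data choose which quantity is estimated, and it is written for one AUC only.

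A reader might infer that the trial's main conclusion is at risk. The documents do not support that: the primary endpoint is change in log10 CFU/mL, and SAP 7.12 treats all secondary endpoints as descriptive. This is a should-fix.

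**What to change.** - In SAP 7.11.2.1 and 7.11.2.2, calculate the trapezoid on log10 CFU/mL, as SAP 2.2 and protocol 5.2 state, and analyse it with the same baseline-adjusted ANCOVA. Dividing by elapsed time would give a result in log10 CFU/mL units.
- Keep log10 of the raw AUC as a supportive analysis for both periods. It is less exposed to the replacement of zeros by 1 CFU/mL, which is the one real drawback of the log-scale AUC.
- Remove the sentence in 7.11.2.1 that makes the log-scale AUC depend on a normality check.
- Make 7.14 consistent for both AUCs. If the raw scale is kept as the main analysis instead, 7.14 should say so for both AUCs and give a reason, and SAP 2.2 should be reworded to match.

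The cost is SAP wording and a few lines of code before unblinding. No new data are needed.

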7.11.2.2 AUC of S. aureus from baseline to post-surgery

An AUC of *S. aureus* CFU/mL including values at all timepoints from baseline to within 1 hour of incision closure will be calculated. This AUC will include the following time points: at baseline, prior to the third dose, immediately prior to surgery and within 1 hour of incision closure. The AUC will be calculated as described in section 6.11.2.1 using the trapezoidal method where the equation will be expanded to include the appropriate post-surgery time point as:

AUC =
$$(t_2-t_1)(a+b) + (t_3-t_2)(b+c) + ... + (t_n-t_{n-1})(r_{n-1}+r_n)$$

where t_n and r_n are the time and the response at the post-surgery timepoint respectively. The AUC will be log_{10} -transformed for analysis. AUC will only be calculated where a patient has non-missing results at all of the following time points: baseline, immediately prior to surgery and within 1 hour of incision closure.

An ANCOVA model will be fitted and presented as described in Section 6.11.1 where the baseline *S. aureus* log₁₀ CFU/mL value will be included as the covariate and treatment group and site as fixed effects.

Summaries

Descriptive statistics will be presented for the pre-surgery AUC and the post-surgery AUC.

Box and whisker plots will be presented for each treatment group for the AUC of *S. aureus* log₁₀ CFU/mL over time.

The calculated AUC values will be listed on both the observed and log₁₀ scale.

7.11.2.3 Change in S. aureus log₁₀ CFU/mL from baseline to post-surgery

The change in *S. aureus* log₁₀ CFU/mL between baseline and post-surgery will be assessed at each of the post-surgery time points (within 1 hour of incision closure, 48 hours after surgery and 6 days after surgery) using an MMRM with visit, treatment group, site and the treatment group by visit interaction as fixed effects, and the baseline *S. aureus* log₁₀ CFU/mL value as a covariate. F-tests from PROC MIXED will be based on Kenward-Roger's adjusted degrees of freedom. The model will include data from all pre and post-surgery visits.

To select the best model, the following variance/covariance matrix structures for the repeated visits within a subject will be assessed: Compound symmetry, 1st order autoregressive, Toeplitz and unstructured. The variance/covariance matrix structure that results in the smallest Akaike information criterion (AIC), indicating the best model fit will be selected.

Results from the MMRM, for the estimate of the effect of each post-surgery time point, will be presented as described in Section 6.11.1. Results from the MMRM, for immediately prior to surgery will also be presented as a sensitivity analysis for the primary analysis (see section 6.11.1).

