6 OVERALL DESIGN AND PLAN OF THE STUDY

6.1 Overview

This is a Phase 2, multi-centre, randomized, double-blind, parallel, placebo-controlled study of multiple applications of a single concentration of XF-73 nasal gel to assess the microbiological effect of XF-73 on commensal *S. aureus* nasal carriage in patients scheduled for surgical procedures deemed to be at high risk of post-operative *S. aureus* infection. The study is divided in 4 periods: screening (Days -14 to -1) randomization (Days -10 to -1), treatment (Days -1 and 0) and follow-up (post-last study dose to Day 30 or Day 90 if an implant is inserted during surgery). Day 0 is the calendar day in which surgery takes place. Only patients who test positive to *S. aureus* by a standardized rapid diagnostic test will be enrolled in the study. Approximately 125 patients will be randomised in a double-blind manner (the investigators and patients are blind to the treatment assignment) in a 1:1 ratio to 0.2% w/w XF-73 nasal gel treatment OR placebo to match XF-73 nasal gel.

The study drug, 0.2% w/w XF-73, or matched placebo will be administered 4 times into each nostril over 24 hours prior to surgery and then a single application immediately upon closure of surgical wound. Additionally, patients may undergo chlorhexidine skin decolonisation ahead of surgery and receive perioperative prophylactic systemic antibiotics in accordance with local practice.

In total 7 nasal swabs will be taken: at screening, 3 times prior to surgery (surgery within 1 hour), post-surgery (right after surgical wound closure), 48 hours post-surgery and 7 days post-surgery.

Efficacy will be assessed by *S. aureus* colonisation from screening to 7 days after surgery as well as by incidence of post-operative staphylococcal infections and use of anti-staphylococcal antibiotics post-surgery. Safety will be assessed by reported AEs from screening up to Day 6 as well as vital signs, physical examination (ENT), clinical laboratory assessments (haematology, clinical chemistry, and urinalysis) and Brief-Smell Identification Tests (B-SIT) at different time points as reflected in [Table 1.1](#).

The maximum study duration will be up to 45 or 105 days for each individual (from screening to post-study follow-up visit) depending on whether a foreign implant was inserted during surgery.

[figure not shown]

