11.10 Determination of Sample Size

Individual CFU data is presented in the study of Verhoeven 2012²⁷ in the absence of treatment. As the primary population for the efficacy analysis is the micro-ITT, those values with zero CFU have been excluded and the resulting data have been converted to the \log_{10} CFU scale. The SD of these values has been used as the estimate of variability for an analysis of change from baseline whilst including baseline \log_{10} CFU as a covariate. As a result, a trial including 80 evaluable patients (40 per arm) would have a greater than 90% power to detect a true treatment effect of a 2 \log_{10} CFU difference and an 90% power to detect a true treatment effect of a 1.5 \log_{10} CFU difference between XF-73 and placebo, assuming 2-sided alpha=0.05, a between patient SD of 2 \log_{10} CFUs taken from the Verhoeven study.

We estimate that approximately 125 patients will need to be recruited in order to have around 80 patients with a burden *S. aureus* nasal carriage which will allow for the detection of an effect of XF-73 nasal gel.

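### The MMRM fits one baseline slope to all five post-baseline visits; if that slope changes over time, the Day 6 estimate, and to a lesser degree the 48-hour estimate, loses precision

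*SAP*

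**What the plan says.** SAP 7.11.2.3 specifies an "MMRM with visit, treatment group, site and the treatment group by visit interaction as fixed effects". Baseline log10 CFU/mL is a covariate and is not crossed with visit. Every pre- and post-surgery visit enters the model: before dose 3, immediately before surgery, closure, 48 hours and Day 6. The covariance structure is chosen by AIC from four candidates.

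Treatment effects are reported for the three post-surgery visits ("within 1 hour of incision closure, 48 hours after surgery and 6 days after surgery"). The pre-surgery estimate from the same model is a sensitivity analysis for the primary endpoint; SAP 7.11.1 says "A Mixed Model for Repeated Measures (MMRM) using all available data will be fitted" for that purpose. The primary analysis is a separate single-time-point ANCOVA with its own baseline slope.

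SAP 7.14 records that, for the change from baseline to post-surgery, "an MMRM model has been chosen in favor of the ANCOVA specified in protocol section 11.7". It does not discuss the form of the baseline adjustment. SAP 7.12 treats all secondary endpoints as descriptive.

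**The concern.** The model lets the treatment effect differ by visit but holds the relation between outcome and baseline constant. On the dosing schedule the first modelled swab comes about 16 hours after baseline (22 h minus 6 h before incision). The last comes about a week after it. Further doses, surgery and possibly systemic prophylaxis lie between. A baseline count often predicts a later count less well as time passes, and nothing in the documents argues that the slope stays constant.

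If the slope does fall, the common slope is drawn towards the early visits and is too steep for the late ones. Two things follow at 48 hours and Day 6: the residual variance is larger than it need be, and part of any chance difference in baseline between the arms stays in the treatment estimate. These are the visits that show whether the effect lasts after surgery, and this MMRM is the only model-based comparison planned for them.

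**Working it through.** **Inputs.** From Protocol 11.10: 40 per arm, and "assuming 2-sided alpha=0.05, a between patient SD of 2" log10 CFU. From Protocol 6.1: 1:1 allocation. From SAP 7.11.2.3: five visits and one baseline slope. The documents give no baseline-to-visit correlations, so every slope below is an assumption. Baseline and visit SDs are set to 2, so slope equals correlation. Data are complete and site is left out.

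**Step 1, the plan's own figure.** The SE of a difference in means is 2 × √(2/40) = 0.447.
- At 1.5 log10: Φ(1.5/0.447 − 1.96) = Φ(1.394) = 91.8% (91.2% with the t distribution). The protocol states "an 90% power to detect a true treatment effect of a 1.5" log10 difference.
- At 2 log10: Φ(4.472 − 1.96) = 99.4%, against a stated figure above 90%.

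The stated power reproduces. It concerns the primary endpoint; none is stated for 48 hours or Day 6.

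**Step 2, formula.** Let b_j be the true slope at visit j and b_c the common slope that the model settles on.
- Own slope at each visit: variance = (2/40) × 4(1 − b_j²).
- Common slope: variance = (2/40) × [4(1 − b_j²) + 4(b_j − b_c)²].
- Ratio = 1 + (b_j − b_c)² / (1 − b_j²).
- Each 1 log10 of baseline imbalance shifts the visit-j difference by b_j − b_c.

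Under unstructured covariance, b_c is the generalised-least-squares average of the b_j, weighted by the inverse residual covariance.

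**Step 3, steeper scenarios.** Residual autoregressive correlation is 0.3 to 0.6.

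| Assumed slopes, before dose 3 to Day 6 | b_c | Ratio, 48 h | Ratio, Day 6 |
|---|---|---|---|
| Equal: 0.5 throughout | 0.50 | 1.00 | 1.00 |
| Mild: 0.7, 0.6, 0.6, 0.5, 0.3 | 0.57–0.58 | 1.01 | 1.08–1.09 |
| Moderate: 0.8, 0.7, 0.6, 0.4, 0.2 | 0.62–0.65 | 1.06–1.08 | 1.19–1.21 |
| Strong: 0.9, 0.8, 0.7, 0.4, 0.1 | 0.75–0.80 | 1.15–1.19 | 1.43–1.49 |

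Example, moderate with b_c = 0.622. Day 6: (0.2 − 0.622)²/0.96 = 0.186, ratio 1.19. 48 hours: (0.4 − 0.622)²/0.84 = 0.059, ratio 1.06. The pre-surgery and closure ratios are at most 1.02 in every row.

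Simulations at 40 per arm gave Day 6 increases of 6–9%, 14–20% and 43–49% for mild, moderate and strong. With a detection floor they gave about 12%, 16% and 44%.

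**Step 4, gentler slopes** (residual correlation 0.6). Power is for a 1.0 log10 effect, common slope versus visit-specific slopes.

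| First to last slope | Variance, 48 h | Variance, Day 6 | Power, 48 h | Power, Day 6 |
|---|---|---|---|---|
| 0.70 to 0.50 | +0.1% | +2% | 79.8 v 79.8% | 72.3 v 73.3% |
| 0.80 to 0.40 | +3% | +10% | 75.1 v 76.3% | 64.1 v 68.4% |
| 0.90 to 0.20 | +14% | +41% | 67.5 v 73.3% | 48.5 v 62.6% |

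At 1.5 log10 the Day 6 figures are 96.9 v 97.2%, 93.6 v 95.5% and 82.2 v 92.8%. If slopes instead rise (0.30 to 0.60), the loss is 1 to 2 points or less.

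**Step 5, bias and imbalance.** In simulation the mean error of the common-slope estimate was at most about 0.02 log10 at 48 hours and Day 6. Type I error under unstructured covariance was 4.4–5.4%. A one-SE chance baseline imbalance is 0.447 log10. In the gentler set it leaves 0.06, 0.13 or 0.28 log10 in the Day 6 difference. In the steeper moderate row it leaves 0.42 × 0.447 = 0.19. A full 1 log10 imbalance would be 1/0.447 = 2.24 SE, an unusual draw.

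**The case against.** The best counter-argument is that early slopes may not be steep here. The first modelled swab already follows two doses, and SAP 7.11 sets undetected counts to 1 CFU/mL, which is 0 on the log scale. Protocol 6.2.1 reports clearance on the 2 mg/g gel of 41.7% after two doses in one volunteer study and 62% after three in another, against 8.3% and 18% on placebo. Patients at the floor flatten the early slopes. If clearance at about those rates is assumed to strike regardless of baseline load and to fall to 20% on active by Day 6, the Day 6 increases in the steeper scenarios drop to about 2%, 5% and 10%. This stands as a reason to expect the lower end. It works by making the slopes more alike, so it moves the trial towards the milder rows. A floor that only truncates low counts leaves the increases nearly intact (Step 3).

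Two limits also stand. The figures assume unstructured covariance, while the SAP chooses by AIC. If compound symmetry were chosen, simulated Day 6 type I error with the common slope was 10.6% (moderate) and 15.8% (strong), but that comes mainly from forcing one variance on all visits and is a separate issue. Site effects and missing data were not modelled.

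Stronger readings that a reader might infer are not supported:
- That the late estimates are biased. Randomisation rules out systematic bias; the shift depends on chance imbalance.
- That they certainly lose power. This needs a slope change that the documents cannot show.
- That the primary result is weakened. Its ANCOVA has its own slope, and the pre-surgery MMRM estimate barely moves.
- That the SAP gave up a planned visit-specific adjustment at 48 hours and Day 6. Protocol 11.7 names an ANCOVA only for the post-surgery measurement, which its AUC items suggest is the closure swab.

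**Conclusion.** The point holds as a conditional loss of efficiency. As written, five visits share one baseline slope. If the slopes are equal, nothing is lost. If they decay, Day 6 variance rises by about 2–12% (mild), 10–20% (moderate) or 40–50% (strong). At 48 hours the rise is mostly 0–4%, 6–8% in the steeper moderate scenario, and about 14–20% under strong decay. In the gentler set, power at 1.0 log10 falls by 1 to 4 points at Day 6 under mild to moderate decay and by about 14 under strong decay.

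These sizes rest on assumed slopes, SD 2 at each visit, 40 per arm, complete data and unstructured covariance. Baseline-independent clearance would push them down. Severity is minor: the affected results are descriptive secondary endpoints with no stated power.

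**What to change.** In SAP 7.11.2.3, add the baseline log10 CFU/mL by visit interaction to the MMRM fixed effects, so that each visit has its own slope. Report the LS means and treatment differences by visit at the overall mean baseline. With no treatment-by-baseline term, the differences do not depend on that value, but the LS means do. Nothing else in the model needs to change for this point.

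The cost is one line of SAP text, one model term and four parameters (five slopes instead of one). With equal slopes the simulations showed no measurable loss. The change should be made before unblinding, so that it cannot look data-driven. If the sponsor prefers the common slope, SAP 7.11.2.3 should say why it is expected to hold from before dose 3 to Day 6.
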